Appendix C. RECIST (v1.1) Criteria

The protocol requires that a PD must be confirmed. The analysis of modified RECIST 1.1 BOR endpoints will follow standard RECIST 1.1 convention which does not require confirmation of PD.

Objective response (OR) per Response Evaluation Criteria in Solid Tumors (RECIST) 1.1

Timepoint Response by Investigator:

Timepoint response by Investigator is the overall tumor response collected on the Overall Response modified RECIST 1.1 CRF at each tumor assessment.

Confirmed BOR by Investigator:

Best Overall Response (BOR) by Investigator is derived from the timepoint response by investigator using RECIST 1.1 criteria. At each time point, BOR will be derived based upon the evaluated time points up to and including the current assessment. The following rules will apply to BOR:

- CR is better than PR; PR is better than SD; SD is better than PD; PD is better than NE.
- For a BOR of SD, a duration of SD \geq 49 days since study day 1 is required.
- For a BOR of CR and PR, confirmation is required **by a repeat assessment at least** \geq 28 days after the initially observed assessment of CR or PR
 - A CR must be confirmed by CR, a PR can be confirmed by a PR or CR.
 - **For confirmation of PR or CR**, an unlimited number of intermittent assessments of NE can occur between the initial response and the confirmation. For example, BL, CR, NE, NE, NE, CR – the CR at post-baseline 1st **assessment** is confirmed at post-baseline 5th **assessment**.
 - **For confirmation of PR**, an unlimited number of intermittent assessments of SD can occur between the initial PR and the confirmation. It is reasonable to consider a patient with time point response of PR-SD-SD-PR as a confirmed response i.e., **confirmed PR**.

[Table 14.1](#) provides the BOR determination per RECIST 1.1 for trials where confirmation of response is required. A BOR determined by [Table 14.1](#) is considered as confirmed

BOR. [Table 14.2](#) outlines the steps to derive Confirmed_BOR (step 1) given investigator's timepoint assessments.

Interim BOR by Investigator:

At interim futility analysis, due to lack of sufficient follow-up time for confirmation scan, study team may choose to report both confirmed responders and unconfirmed responders (subjects had an initial PR or CR and still has potential for future confirmative scans). Interim BOR is defined to include unconfirmed responders in addition to those who achieve confirmed BOR.

Timepoint Response by Central Review:

Timepoint response by Central Review is the Overall response at each tumor assessment as assessed by Central radiographic reader(s). This data is usually non-CTDB dataset transferred from Central Review vendor.

Confirmed BOR by Central Review:

Confirmed BOR by Central Review will be derived from the Timepoint Response by Central Review in the same way as Confirmed BOR by Investigator.

Interim BOR by Central Review:

Interim BOR by Central Review will be derived from Timepoint response by Central Review in the same way as Interim BOR by Investigator.

Best Overall Response (BOR):

The best overall response is the best observed disease response recorded from the start of the study treatment until disease progression/recurrence, the start of new anticancer therapy or the end of study. Confirmed BOR by Investigator, Interim BOR by Investigator, Confirmed BOR by Central Review, Interim BOR by Central Review have been separately defined above.

The followings steps would be followed to derive ORR as per RECIST 1.1.

Table 14.1. BOR per RECIST 1.1 where confirmation of CR/PR is required

[figure not shown]
Criterion	Time point T1 Response	T1 ≥ 49 days after Baseline?	Time point T2 Response	T2 ≥ 49 days after Baseline?	T2 ≥ 28 days after T1?	Confirmation	
C1	CR	Yes	CR	-	Yes	CR	
C2			CR	-	No	SD	
C3			PR, SD	-	-	Query data*	
C4			PD	-	-	SD	
C5			NE, No further evaluations			SD	
C6		No		CR	-	Yes	CR
C7				CR	Yes	No	SD
C8				PR, SD	-	-	Query data*
C9				PD	-	-	PD
C10				NE, No further evaluations			NE
C11	PR	Yes	CR, PR	-	Yes	PR	
C12			CR, PR	-	No	SD	
C13			SD	-	-	SD	
C14			PD	-	-	SD	
C15			NE, No further evaluations			SD	
C16		No		CR, PR	-	Yes	PR
C17				CR, PR	Yes	No	SD
C18				SD	Yes	-	SD
C19				PD	-	-	PD
C20				NE, No further evaluations			NE
C21	SD	Yes	CR, PR, SD, PD, NE, no more evaluation			SD	
C22			No	CR, PR, SD	Yes	-	SD
C23		CR, PR, SD		No	-	NE	
C24		PD		-	-	PD	
C25		NE, No further evaluations			NE		
C26	PD		-		PD		
C27	NE	-	NE, No further evaluations			NE	
C28		-	CR, PR, SD	Yes	-	SD	
C29		-	CR, PR, SD	No	-	NE	
C30		-	PD	-	-	PD	

CR = complete response, PR = partial response, SD = stable disease, PD = progressive disease, and NE = not evaluable.

*If a CR is truly met at first time point, then any disease seen at a subsequent time point, even disease meeting PR criteria relative to baseline, makes the disease PD at that point (since disease must have reappeared after CR). Best response would depend on

whether minimum duration for SD was met. However, sometimes 'CR' may be claimed when subsequent scans suggest small lesions were likely still present and in fact the patient had PR, not CR at the first time point. Under these circumstances, the original CR should be changed to PR and the best response is PR.

Note: The UE response collected on eCRF will be mapped to NE for all the derivations and analysis.

Deriving Objective Response Rate (ORR) per RECIST 1.1

ORR is defined as the proportion of subjects with Objective Response while on study as defined by RECIST 1.1. All subjects that do not meet the criteria for objective response by the analysis cut-off date will be considered as non-responders.

$$\text{ORR} = (\text{Number of Subjects with Objective Response}) / \text{Total number of subjects in the analysis set.}$$

Note: Study allows NE between CR and its confirmation scan (CR-NE-CR), and NE/SD between PR and its confirmation scan (PR-SD-PR or PR-NE-PR).

Note: We will be deriving two sets of ORR and **presenting**, namely Objective Response Rate by Central Review and Objective Response Rate by Investigator Review.

Unconfirmed Responses for Interim Analysis

For a study where CR/PR confirmation is required, due to lack of sufficient follow-up time at interim analysis, both confirmed responders and unconfirmed responders will be reported. Subjects with any objective response (i.e., CR or PR) that is not confirmed as defined in [Section 5.1.2](#) will be summarized based on below definitions.

Interim response of unconfirmed CR awaiting confirmatory scan:

A subject will have an interim response of unconfirmed CR awaiting confirmatory scan if and only if each of the following requirements is met: 1) the confirmed best overall response is not a confirmed CR and 2) the last evaluable tumor assessment prior to data cutoff (DCO) is a CR and 3) none of the following events are recorded (end of study date, death date, new anti-cancer therapy, end of radiographic follow up date, progression date).

Interim response of unconfirmed PR awaiting confirmatory scan:

A subject will have an interim response of unconfirmed PR awaiting confirmatory scan if and only if each of the following requirements is met: 1) the confirmed best overall response is not a confirmed CR and not a confirmed PR and 2) the last evaluable non-SD tumor assessment prior to data cutoff (DCO) is a PR and 3) none of the following events are recorded (end of study date, death date, new anti-cancer therapy, end of radiographic follow up date, progression date).

Interim response of unconfirmed response awaiting confirmatory scan:

A subject will have an interim unconfirmed response awaiting confirmatory scan if the subject has either an unconfirmed PR or an unconfirmed CR, awaiting a confirmatory scan.

Interim response of unconfirmed CR and not confirmed at next evaluable scan:

A subject will have an interim response of unconfirmed CR and not confirmed at next evaluable scan if and only if each of the following requirements is met: 1) the confirmed best overall response is not a confirmed CR and 2) any evaluable tumor assessment prior to data cutoff (DCO) is a CR and 3) either of the following occurs:

- A CR is recorded at the last evaluable tumor assessment and any of the following events are recorded (end of study date, death date, new anti-cancer therapy, end of radiographic follow up date, progression date) or
- For any CR recorded prior to the last evaluable tumor assessment, the subsequent evaluable tumor assessment is never a CR.

Interim response of unconfirmed PR and not confirmed at next evaluable scan:

A subject will have an interim response of unconfirmed PR and not confirmed at next evaluable scan if and only if each of the following requirements is met: 1) the confirmed best overall response is not a confirmed CR and not a confirmed PR and 2) the subject does not have an interim response of unconfirmed CR and 3) any evaluable tumor assessment prior to data cutoff (DCO) is a PR and 4) either of the following occurs:

- A PR is recorded at the last evaluable non-SD tumor assessment and any of the following events are recorded (end of study date, death date, new anti-cancer therapy, end of radiographic follow up date, progression date) or
- For any PR recorded prior to the last evaluable non-SD tumor assessment, the subsequent evaluable tumor assessment is never a PR or CR.

Interim response of unconfirmed response and not confirmed at next scan:

A subject will have an interim unconfirmed response and not confirmed at next scan if the subject is classified as either unconfirmed PR or an unconfirmed CR, not confirmed at next scan.

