^e If tocilizumab is not available, siltuximab (an anti-IL-6 monoclonal antibody) may be used in the management of cytokine release syndrome, following the criteria outlined in the Management of Adverse Events table. The recommended dose of siltuximab is 11 mg/kg administered over 1 hour as an intravenous infusion, consistent with the prescribing information for the treatment of multicentric Castlemans disease (Sylvant Prescribing Information), and the CARTOX Working Group Guidelines for CRS management (Neelapu, 2018). Siltuximab may be repeated if needed, in the event that CRS recurs after a subsequent infusion of AMG 160. Siltuximab may not be repeated in an individual subject that develops anaphylaxis to siltuximab, or gastrointestinal perforation after siltuximab.

^f A subgroup analysis for subjects treated with siltuximab will be evaluated, including CRS outcomes, safety, and PK data.

11.11 **Appendix 11. Performance Status According to Eastern Cooperative Oncology Group (ECOG)**

ECOG Performance Status Scale	
Grade	Descriptions
0	Fully active, able to carry on all pre-disease performance without restriction
1	Restricted in physically strenuous activity but ambulatory and able to carry out work of a light or sedentary nature, eg, light house work, office work
2	Ambulatory and capable of all selfcare but unable to carry out any work activities. Up and about more than 50% of waking hours
3	Capable of only limited selfcare, confined to bed or chair more than 50% of waking hours
4	Completely disabled. Cannot carry on any selfcare. Totally confined to bed or chair
5	Dead

ECOG = Eastern Cooperative Oncology Group.

Source: Oken et al, 1982

11.12 Appendix 12. Response Evaluation Criteria in Solid Tumors Version 1.1 (modified RECIST 1.1)

Response Evaluation Criteria in Solid Tumors version 1.1 (RECIST 1.1) are guidelines for assessing tumor burden changes in response to treatment (Eisenhauer et al, 2009). Additional patterns of response have been observed with immune-enhancing therapies, including delayed clinical response, leading to criteria modifications to capture treatment responses more accurately (Wolchok JD et al, 2009; Nishino M et al, 2013). This study utilizes modified RECIST 1.1 criteria which applies aspects of the immune-related response criteria (including requiring confirmation of disease progression) to RECIST 1.1 as outlined below.

Modified RECIST 1.1 tumor response assessment

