- Complete Response (CR) – disappearance of all measurable lesions
 - Pathologic lymph nodes must have reduction in short axis to < 10 mm
- Partial Response (PR) – decrease of 30% or greater in tumor burden compared with baseline
- Stable Disease (SD) - not meeting the criteria for CR, PR, or progressive disease
- Progressive Disease – increase of 20% or greater in tumor burden compared with nadir, or the appearance of one or more new lesions

Non-target lesion response:

- CR – disappearance of all non-**target** lesions
 - Pathologic lymph nodes must have reduction in short axis to < 10 mm
- SD – persistence of one or more non-**target** lesions, not meeting the criteria for CR or progressive disease
- Progressive disease – unequivocal progression of existing non-**target** lesions, or the appearance of one or more new lesions

Overall response:

- CR
 - Complete disappearance of all lesions
 - Pathologic lymph nodes must have reduction in short axis to < 10 mm
 - Confirmation scan required - repeat, consecutive assessment no less than 4 weeks from the date of the first documented response
 - CR is dated at time of confirmation scan
- PR
 - Decrease in tumor burden $\geq 30\%$ relative to baseline, or
 - Complete disappearance of all **target** lesions with presence of non-**target** lesions
 - Confirmation scan required - repeat, consecutive assessment no less than 4 weeks from the date of the first documented response
 - PR is dated at time of confirmation scan
- SD
 - **Target** lesions not meeting criteria for CR, PR or progressive disease, or
 - In subjects with only non-**target** disease, persistence of one or more non-**target** lesions
- Progressive Disease
 - Radiologic detection of $\geq 20\%$ increase in tumor burden relative to nadir and at least 5 mm absolute increase, or
 - Unequivocal progression of non-**target** lesions, or
 - The presence of new lesions
 - Confirmation scan required - repeat, consecutive assessment 4-6 weeks from the date of the first documented response
 - Radiographic progressive disease is confirmed at repeat imaging (progressive disease on two consecutive scans 4-6 weeks apart) if:
 - Tumor burden remains increased by $\geq 20\%$ and at least 5 mm absolute increase relative to nadir, or
 - Unequivocal progression of non-**target** lesions is observed, or
 - New lesions are present

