2.1 Objectives and Endpoints/Estimands

Objectives	Endpoints

 Primary 	

 To evaluate the safety and tolerability of AMG 160 To evaluate the maximum tolerated dose (MTD) or the recommended phase 2 dose (RP2D) 	
 Dose-limiting toxicities (DLT) Treatment-emergent adverse events Treatment-related adverse events Changes in vital signs, electrocardiograms (ECGs), and clinical laboratory tests

 Secondary 	

 To characterize the pharmacokinetics (PK) of AMG 160 	
 PK parameters for AMG 160 following intravenous (IV) administration including but not limited to, maximum serum concentration (C_{max}), minimum serum concentration (C_{min}), area under the concentration-time curve (AUC) over the dosing interval, accumulation, and half-life (t_{1/2})

 To evaluate the preliminary anti-tumor activity of AMG 160 	
 Objective response (OR) per modified Response Evaluation Criteria in Solid Tumors (RECIST) 1.1 Overall Survival Progression-free survival (radiographic, clinical) Time to response Time to progression (radiographic, clinical) Duration of response Time to subsequent therapy

Exploratory

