2.2 Hypotheses and/or Estimations

No formal statistical hypotheses will be tested.

3. Study Overview

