Details about the censoring rules are included in [Appendix E](#).

Radiographic Progression:

Disease progression per RECIST 1.1 occurs.

Radiographic Progression-free Survival (radiographic PFS):

Radiographic PFS is defined as the interval from Study Day 1 to the earlier of a radiographic progression or death from any cause; otherwise **PFS is censored based on criteria in [Appendix E](#)**.

Clinical Progression:

Clinical disease progression is based on clinical symptoms and are not associated with radiologic progression.

This is recorded by the field ‘disease progression is equal to clinical progression’ on the EOIP eCRF page.

Details about the censoring rules are included in [Appendix E](#).

Clinical Progression-free Survival (clinical PFS):

Clinical PFS is the time from Study Day 1 to clinical disease progression or death from any cause.

Details about the censoring rules are included in [Appendix E](#).

Time to Response (TTR):

TTR is defined as the time from the date of Study Day 1 to the date of the first documented CR or PR that is subsequently confirmed per RECIST1.1. For a subject who did not respond, time to response will be censored at the latest evaluable radiological assessment date. If a subject has no tumor evaluation in the study, time to response will be censored at the date of Study Day 1.

The time of the initial response will be defined as the earliest of the dates contributing towards the first visit response of PR or CR.

- For confirmed responders whose PR or CR are confirmed in two **evaluable** assessments, the first PR/CR assessment among the two **evaluable** assessments will be used to calculate TTR.
- For unconfirmed responders awaiting follow-up confirmation scans, the PR or CR assessment that is awaiting confirmation scan will be used to calculate TTR.

Time to Radiographic Progression:

Time to radiographic progression is defined as the interval from Study Day 1 to radiographic progression; otherwise, time to radiographic progression is censored based on the criteria in [Appendix E](#).

Time to Clinical Progression:

Time to clinical progression is defined as the interval from Study Day 1 to clinical progression; otherwise, time to clinical progression is based on the criteria in [Appendix E](#).

Subsequent Therapy:

Subsequent therapy is defined as subjects receiving anti-cancer therapies intended to treat NSCLC or any other anti-cancer therapies prior to end of study.

Time to Subsequent Therapy:

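### The SAP scores objective response without confirmation of progression, although the endpoint and the Part 2 gate are named per modified RECIST 1.1, which requires it

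*SAP*

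**What the plan says.** **Protocol.** Appendix 12 (Section 11.12) explains why the criteria were modified: "Additional patterns of response have been observed with immune-enhancing therapies, including delayed clinical response, leading to criteria modifications to capture treatment responses more accurately". It says that the study's version "applies aspects of the immune-related response criteria (including requiring confirmation of disease progression) to RECIST 1.1". The operative rule follows under overall response: "Radiographic progressive disease is confirmed at repeat imaging (progressive disease on two consecutive scans 4-6 weeks apart) if" one of three listed findings is present. Section 8.2.2 repeats the requirement for a second scan at 4 to 6 weeks. The study schema continues treatment until progression is confirmed.

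**Where the modified criteria are named.** SAP 2.1 lists the endpoint as "Objective response (OR) per modified Response Evaluation Criteria in Solid Tumors (RECIST) 1.1", as does Protocol Section 3. SAP Table 9-1 uses the same label. Protocol 4.1 and 4.2 and SAP 3.1 open Part 2 on one or more objective responses per modified RECIST 1.1.

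**How the SAP scores it.** Appendix C acknowledges the protocol's requirement and then sets it aside: "The analysis of modified RECIST 1.1 BOR endpoints will follow standard RECIST 1.1 convention which does not require confirmation of PD". It closes the response window at progression: "The best overall response is the best observed disease response recorded from the start of the study treatment until disease progression/recurrence". Row C26 of Table 14.1 gives a first PD a best overall response (BOR) of PD. Anyone who does not meet objective response by the cut-off is a non-responder. For radiographic progression, SAP 5.1.2 says only "Disease progression per RECIST 1.1 occurs". Appendix E uses the date of PD for radiographic PFS, time to progression (TTP) and duration of response (DOR), with no confirmation step.

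**Section 10 (changes from protocol).** It lists the new RECIST 1.1 evaluable set and the change of terminology for radiographic PFS, and ties that endpoint to RECIST 1.1. It does not mention confirmation of PD, and it says nothing about the change for BOR or the objective response rate (ORR). No analysis with confirmed PD is planned.

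**The concern.** One label covers two different rules. The protocol keeps a subject on treatment and under imaging after a first PD so that the next scan can confirm or refute it. The SAP then scores response as if that next scan did not exist.

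Two things are at stake. The first is meaning: an ORR reported per modified RECIST 1.1 would have been derived by standard RECIST 1.1. The second is a decision. The Part 2 gate and the futility count are meant to be the same test at 10 subjects, but as written they can give different answers for the same subject.

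**Working it through.** **1. One subject under each rule.** Take PD at the first scan from target-lesion growth, no new lesions, a next scan that no longer meets PD, and then a partial response measured against baseline and confirmed at least 4 weeks later.

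| Item | Protocol Appendix 12 | SAP Appendix C, 5.1.2, Appendix E |
|---|---|---|
| First PD | Not confirmed | Counts as PD |
| Later confirmed PR | Response (implied) | After the BOR window has closed |
| Objective response | Yes | No |
| Radiographic PFS and TTP | No event at the first PD | Event at the first PD |
| Part 2 gate, named per modified RECIST 1.1 | Met | Not met if Appendix C is applied |
| Table 7-3 count | 1 | 0 |

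The interim category for unconfirmed responses does not recover this subject. Appendix C bars it once a progression date is recorded.

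**2. Reproduce the futility boundary.** Inputs from SAP 7.1: prior Beta(0.5, 0.5), target ORR above 15%, pT = 0.25, 50 evaluable subjects, stop if the predictive probability is below 30%.

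- End-of-study success: P(ORR > 0.15 | x of 50) > 0.25, with posterior Beta(x + 0.5, 50.5 − x). This probability is 0.161 at x = 5 and 0.287 at x = 6, so success means at least 6 of 50.
- Predictive probability with s responders among n: the beta-binomial probability, with parameters s + 0.5 and n − s + 0.5, that the remaining 50 − n subjects bring the total to 6 or more.

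| n | Stops at | Predictive probability | Continues at | Predictive probability |
|---|---|---|---|---|
| 10 | 0 | 0.095 | 1 | 0.495 |
| 20 | 1 | 0.133 | 2 | 0.438 |
| 30 | 2 | 0.116 | 3 | 0.383 |
| 40 | 3 | 0.066 | 4 | 0.301 |

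This reproduces Table 7-3 (fewer than 1, 2, 3 and 4). At each look one responder separates stop from continue, so the scoring rule can matter.

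**3. Size, under an assumption.** Let f be the share of true responses that occur only after a first, unconfirmed PD. The documents give no value, so f = 5% to 30% is assumed. Every response is also assumed to be visible at the look. The SAP rule counts responses at rate ORR × (1 − f), so P(0 of 10) = (1 − ORR(1 − f))^10. At ORR 20%, f = 0 gives 0.80^10 = 10.7% and f = 30% gives 0.86^10 = 22.1%. The chance of crossing the boundary at any of the four looks comes from exact binomial recursion over n = 10, 20, 30 and 40.

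| f | P(0/10), ORR 20% | Any look, ORR 20% | P(0/10), ORR 15% | Any look, ORR 15% |
|---|---|---|---|---|
| 0 | 10.7% | 15.3% | 19.7% | 32.0% |
| 5% | 12.2% | 17.8% | 21.5% | 35.6% |
| 10% | 13.7% | 20.6% | 23.5% | 39.4% |
| 20% | 17.5% | 27.7% | 27.9% | 48.0% |
| 30% | 22.1% | 36.8% | 33.0% | 57.6% |

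The boundaries do not move. Only the count entered into them does.

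**The case against.** The strongest reply is that this is an open, prespecified choice in an exploratory study. Appendix C names the protocol's rule before departing from it, standard RECIST 1.1 compares more easily with other trials, and the SAP states that "No formal statistical hypotheses will be tested". That stands in part: which version leads is partly preference. It does not justify keeping the modified label on the standard derivation, leaving the BOR and ORR change out of Section 10, or planning no analysis on the named criteria.

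Several stronger readings are tempting, and the documents do not support them.

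- *All delayed responses are lost.* No. A late response after stable disease still counts if confirmed, and so does one after growth below the PD threshold. Only responses after a first PD are lost.
- *The protocol states that a response after an unconfirmed PD counts.* It implies this, because response is measured from baseline and PD needs confirmation, but Appendix 12 gives no explicit BOR rule for the case. Persisting new lesions remain PD whatever the target lesions do.
- *One reclassified subject decides whether Part 2 opens.* The futility rule says the study may stop. The Part 2 gate is stated separately for Part 1, which may also include up to 20 backfill subjects.
- *PFS events fall at least 8 weeks early.* That is not a minimum. Death is an event at any time, scans may be brought forward, and a first PD with no follow-up scan could reasonably keep its first date.
- *The activity objective cannot be answered.* The confirming scans are required and timepoint responses are collected on a modified RECIST 1.1 form, so the protocol version can still be derived.

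Timing also limits the effect at the first look. After PD at week 8, the confirming scan falls at weeks 12 to 14. A response first seen there needs a repeat at least 4 weeks later, at week 16 to 18 or beyond, which is about month 4. Some such responses would therefore not yet be confirmed under either rule.

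**Conclusion.** The mismatch is in the text and should be fixed before the analyses are run. The endpoint and the Part 2 gate are named by criteria that require confirmation of PD, and Appendix C scores response by criteria that do not. The same step is missing for radiographic PFS, TTP and DOR. In the endpoint tables only objective response carries the modified label, so for these three the point is inconsistency with the protocol's definition of radiographic progression rather than a wrong label. Overall survival is unaffected.

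The size is unknown. It depends wholly on how often a response follows an unconfirmed PD, which the documents do not give. Under the assumed 5% to 30%, at a true ORR of 20%, P(0 of 10) rises from 10.7% to 12.2–22.1%, and the chance of meeting the futility boundary at any look rises from 15.3% to 17.8–36.8%. If such responses do not occur, the two versions of ORR agree. This is a should-fix point: it changes what the reported ORR means and could change a close, non-binding decision.

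**What to change.** - In SAP Appendix C and 5.1.2, add a derivation of BOR, ORR, radiographic PFS, TTP and DOR by Protocol Appendix 12: a PD counts, and closes the BOR window, only if confirmed. State how a first PD with no follow-up scan is handled, for example as PD at the first date. Carry this into the Appendix E censoring tables and the interim response categories.
- Use that version wherever the documents say per modified RECIST 1.1, including the Part 2 gate in SAP 3.1 and the Table 7-3 count.
- Report the standard RECIST 1.1 version alongside under its own name, and correct the label in Table 9-1.
- List the standard RECIST 1.1 derivation in Section 10 as a departure, with the reason.
- Reconcile the PD definition in SAP Appendix D, which still speaks of confirmation but only for new lesions.

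The cost is SAP wording and one further derivation from scans the protocol already requires. The downside is two versions of each radiographic endpoint, and the protocol version compares less directly with results from trials that used standard RECIST 1.1.

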8.2.2 Efficacy Assessments

Efficacy will be determined by radiographic assessments.

Radiographic assessments will be obtained as scheduled in [Table 1-6](#) irrespective of cycle duration including dose delays and treatment discontinuation.

Standard radiological assessments should take place until clinically significant disease progression or deterioration, withdrawal of consent, or start of new anticancer therapy. Every assessment must include the chest, abdomen, and pelvis, all other known sites of disease and magnetic resonance imaging (MRI) of the brain if a subject has signs or symptoms suggestive of CNS metastases. The MRI/CT can be obtained earlier if clinical deterioration necessitates an earlier scan at the discretion of the managing physician. The same contrast and modality used at screening should be used for all subsequent assessments. [REDACTED]

[REDACTED]

Tumor burden assessments will be performed based on modified RECIST 1.1 criteria. To confirm PD, a second MRI/CT scan must be performed 4 to 6 weeks after the first detection of radiographical progression. Responses (PR and complete response [CR]) require confirmation by a repeat consecutive assessment at least 4 weeks after the first detection of radiographical response. Refer to the imaging manual for details on imaging assessments.

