CR = complete response; NA = not available; ND = not done; PR = partial response; RECIST = Response Evaluation Criteria in Solid Tumors; SD = stable disease; UE = unable to evaluate

^a Decrease assessed relative to baseline. Increase assessed relative to nadir.

^b Response: CR and PR require a confirmation assessment after ≥ 4 weeks, may also wait until the next scheduled imaging

^c Progression: Progressive disease requires a confirmation assessment 4-6 weeks after initial radiographic progressive disease is observed

^d Subjects with non-**target** lesions only

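### The SAP confirms a PR across any number of SD scans although the protocol requires consecutive confirmation; this undeclared change can raise ORR and can alter the futility count

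*SAP*

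**What the plan says.** **Protocol.** Section 8.2.2 says that PR and CR "require confirmation by a repeat consecutive assessment at least 4 weeks after the first detection of radiographical response". Appendix 12 (Section 11.12) repeats this under overall response, for CR and for PR: "Confirmation scan required - repeat, consecutive assessment no less than 4 weeks from the date of the first documented response". A footnote to the summary table in that appendix adds "CR and PR require a confirmation assessment after ≥ 4 weeks, may also wait until the next scheduled imaging". No protocol text allows an SD scan between a PR and its confirmation.

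**SAP, confirmed response.** Appendix C states that "an unlimited number of intermittent assessments of SD can occur between the initial PR and the confirmation" and gives an example: "It is reasonable to consider a patient with time point response of PR-SD-SD-PR as a confirmed response". The note in its ORR derivation repeats the allowance: "NE/SD between PR and its confirmation scan (PR-SD-PR or PR-NE-PR"). The word consecutive is also absent from the definitions in SAP Section 5.1.2 and Appendix D.

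**SAP, interim response.** Appendix C says "Interim BOR is defined to include unconfirmed responders in addition to those who achieve confirmed BOR". One condition for an unconfirmed PR that is still awaiting its scan is that "the last evaluable non-SD tumor assessment prior to data cutoff (DCO) is a PR". The matching definition for CR uses the last evaluable scan and does not skip SD.

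**SAP, declared changes.** Section 10 lists two items: the added RECIST 1.1 evaluable set and the naming of radiographic PFS. Appendix C openly departs from the protocol on confirmation of PD, but makes no such statement about confirmation of PR.

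**The concern.** The two documents define a confirmed PR differently, and a reader of SAP Section 10 would not learn this. Two things are at stake.

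- **ORR.** Subjects whose PR was followed by SD and who later show a single PR scan are responders under the SAP but not under the protocol.
- **Futility.** The first look continues on a single responder among 10 and opens enrolment of up to 40 more subjects. With so low a threshold, the classification of one subject can decide the result. The interim definition keeps PR-then-SD in the awaiting group, so a PR whose next scan did not confirm it may supply that one responder.

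**Working it through.** **1. Which scan sequences differ.** Each scan is taken to be at least 28 days after the one before.

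| Sequence | Protocol (consecutive) | SAP Appendix C |
|---|---|---|
| PR-PR | confirmed | confirmed |
| PR-SD-PR | not confirmed | confirmed |
| PR-SD-SD-PR | not confirmed | confirmed |
| PR-SD-PR-PR | confirmed (last two scans) | confirmed |
| PR-NE-PR | not addressed | confirmed |

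Every sequence that meets the protocol rule also meets the SAP rule, and the reverse is not true. For a given set of scans, the SAP rule can add responders but never remove one.

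**2. What is possible at the first look.** Protocol Table 1-6 schedules CT/MRI every 8 weeks, ±7 days. Four months is 4 × 365.25/12 = 121.75 days, or 17.4 weeks. A subject just reaching month 4 therefore has scheduled scans at weeks 8 and 16; the next is due at week 24. Confirmed PR-SD-PR needs weeks 8, 16 and 24, and PR-SD-SD-PR needs week 32 as well. On scheduled scans neither can be present at month 4, only in subjects followed for longer.

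The route open at month 4 is the interim category. Take PR at week 8, SD at week 16, and no death, progression, new therapy or end of follow-up:

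- Confirmed BOR is neither CR nor PR: met.
- The last evaluable scan, ignoring SD, is a PR (week 8): met.
- No terminating event is recorded: met.

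The subject is classed as awaiting confirmation. The companion category, for PRs not confirmed at the next evaluable scan, does not capture this subject. It needs either a terminating event or a PR that precedes the last non-SD scan, and here the PR is the last non-SD scan.

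**3. Reproducing the futility boundaries (protocol Table 9-3, SAP Table 7-3).** The inputs are prior Beta(0.5, 0.5), N = 50, ORR threshold 15%, predictive probability (PP) cut-off 30%, and pT = 0.25 read as the final posterior threshold.

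- Final success: P(p > 0.15 | X of 50) > 0.25, which requires X ≥ 6.
- PP(x, n) = P(Y ≥ 6 − x), with Y ~ beta-binomial(50 − n, 0.5 + x, 0.5 + n − x).
- Stop if PP < 0.30.

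The minimum counts to continue come out as 1, 2, 3 and 4, exactly as stated.

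| n | Responders without the extra subject | PP | Responders with the extra subject | PP |
|---|---|---|---|---|
| 10 | 0 | 0.095 | 1 | 0.495 |
| 20 | 1 | 0.133 | 2 | 0.438 |
| 30 | 2 | 0.116 | 3 | 0.383 |
| 40 | 3 | 0.066 | 4 | 0.301 |

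At every look, one responder who puts the count on the boundary moves PP across 0.30. If final success is read instead as an observed ORR above 15% (at least 8/50), the minimum counts are 1, 3, 4 and 6. Only the first look then matches the table, but that look still turns on one subject (PP 0.050 against 0.335).

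**4. Size for ORR.** The plan's own example, 20% of 40, is 8/40, with a Clopper-Pearson interval of 9.1% to 35.6% (stated as 9% to 36%). Removing one responder gives 7/40 = 17.5%, interval 7.3% to 32.8%, a shift of 2.5 percentage points.

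**5. Illustration on assumed rates.** The chance of no responder among 10 is (1 − p)^10: 0.60 at p = 5%, 0.35 at 10% and 0.20 at 15%. If the looser count raised the counted rate from 5% to 10%, the chance of stopping at the first look would fall from 0.60 to 0.35. Those rates are assumptions; the documents give no frequency for the pattern.

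**The case against.** The other side has fair points. ORR is a secondary endpoint, no hypothesis is tested, and the futility rule is permissive: the study may stop. SAP Section 5.1.2 requires confirmation for an objective response, so the objective responder in the futility rule could mean a confirmed one. The SD allowance is stated twice in Appendix C, so it looks deliberate, and the protocol's summary table speaks of a subsequent rather than a consecutive assessment. Declaring the rule in Section 10 would end the discrepancy.

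These points limit the consequence and make declaration an acceptable alternative. They do not reconcile the documents. Section 8.2.2 and the overall-response definitions in Appendix 12 both say consecutive, and the footnote on timing lets confirmation wait for the next scheduled scan, not pass over one.

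A reader might also infer four stronger things that the documents do not support.

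- **That the futility count does include such subjects.** Appendix C says in one place that the team may choose to report unconfirmed responders, and in another that both kinds will be reported. Neither statement says which BOR is compared with Table 7-3. Inclusion is possible, not stated.
- **That PR-SD-SD-PR could rescue the first look in a subject just reaching month 4.** The scheduled scans do not allow it.
- **That Table 14.1 row C13, which scores PR then SD as SD, contradicts the SD allowance.** The table covers two time points, and PR then SD with nothing further is SD under either rule. A later PR is a third time point that the row does not address. Table 14.2, cited for the derivation, is not in the text available, so the rule for longer sequences cannot be checked.
- **That the rule inflates DOR by counting SD time as response.** DOR runs from first response to progression or death, so SD time counts under any confirmation rule. The confirmation rule changes who enters the DOR analysis, not how time is counted.

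**Conclusion.** The point holds as an undeclared difference between protocol and SAP in the definition of a confirmed PR, together with an open question about which response count drives futility. Any effect on ORR is upward: 2.5 percentage points per affected subject among 40. For futility, one PR-then-SD subject can change stop to continue when the count sits on the boundary, most plainly at 0/10 against 1/10 (PP 0.095 against 0.495).

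This rests on reading consecutive in its ordinary sense, on pT = 0.25 as the final posterior threshold (which reproduces the table exactly), and, for futility, on interim BOR being the count used, which the SAP leaves open. The expected size across the trial cannot be given because the frequency of the pattern is unknown. The change should be made, since following the SAP as written can give a different ORR and go/stop count from the protocol's endpoint.

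**What to change.** 1. In SAP Appendix C, apply the protocol's consecutive rule to the ORR and futility counts: the next evaluable scan at least 28 days later must be PR or CR. Align the note in the ORR derivation.
2. List the allowance for intervening NE scans in SAP Section 10. It is the SAP's own; the protocol does not state it.
3. Delete the non-SD qualifier from the interim PR definitions, so that PR followed by SD is no longer classed as awaiting confirmation.
4. State whether confirmed or interim BOR is compared with Table 7-3.
5. Report ORR under the SD-tolerant rule as a sensitivity analysis. If the sponsor prefers to keep that rule as primary, declare it in Section 10 and report ORR under the protocol rule beside it.

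The cost is SAP wording and one additional ORR derivation. No boundary or sample size changes. ORR may be slightly less favourable.
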